- QMF149 150/80 microgram o.d. delivered via Concept1
- MF 200 microgram o.d. delivered via Twisthaler®

Randomized patients must have FEV_1 between 60% and < 90% of predicted normal at **both** Visit 101 and Visit 102 and they must qualify for treatment with low dose ICS plus LABA as per GINA 2016 guidelines. At Visit 102, **all** randomized patients must have $ACQ-7 \ge 1.5$. Refer to Section 4.1 Inclusion Criteria for ACQ-7 requirements.

Visit 102 (end of Run-in) and Visit 201(Randomization) must take place sequentially on the same day. The assessments at Visit 102 should be performed prior to administration of the first dose of study medication (Visit 201). Reversibility should NOT be done at Visit 102 (Table 6-1). Randomized patients will enter the 12-week Treatment epoch. All patients will receive both Concept1 and Twisthaler® inhalers (double-blind and double-dummy design). During the treatment epoch, patients will be instructed to inhale study medication once daily in the evening (between 5:00 pm and 8:00 pm).

[figure not shown]
Patients will be followed at regular intervals throughout the 12 week treatment epoch to assess the safety and efficacy of treatment, either by telephone or at clinic visits. Clinic visits are scheduled to take place after 4, and 12 weeks. All clinic visits should occur as scheduled per Table 6-1. Patients will be required to attend the clinic visits to perform trough measurements of lung function (24 hours post dosing) after the first dose of study medication (Visit 201) and after the dose of study medication administered at the clinic after 12 weeks of treatment (Clinic Visit 204). In case of logistical issues, Visit 204 (Week 12) should take place within a 4 day window. If this is not possible, the sponsor should be notified.

Pre-dose FEV_1 measurements will be assessed at Week 4. Telephone reviews of patients' status will be conducted after 8 weeks of treatment. Telephone contact with patients may indicate that a clinic visit is necessary, in which case an unscheduled clinic visit should be arranged as soon as possible and should include safety assessment (AEs, concomitant medications review and unscheduled laboratory exams as appropriate).

A final telephone contact must be conducted at 30-days after last treatment date (telephone Visit 301 or unscheduled visit safety call for patients who discontinue treatment earlier than 12 weeks).

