In this Phase III study, randomized patients will receive either QMF149 or MF throughout the treatment epoch (12 weeks). Throughout the trial, patients will be given access to rescue medication (i.e., short acting beta-2agonist (SABA)), thus limiting the risk of significant asthmatic AEs. At no time during the study will any patient be without treatment for asthma.

The risk to the patients in participating in this study is that QMF149 is under development and therefore unexpected safety issues may be possible in patients randomized to QMF149 treatment (Section 5.6.2). This risk will be minimized by adherence to the patient eligibility criteria as stated in the study protocol and by close clinical monitoring of all patients. The risks of side effects from the study medication are those known for the individual compounds indacaterol and MF, and no additional risks have been identified that might occur when the two components are administered concurrently or from the same inhaler. Further information can be obtained from the most current QMF149 Investigator's Brochure.

There is evidence that LABA treatment used alone in asthma might cause asthma exacerbations (FDA warning, Advair® Diskus® prescription information). This risk is mitigated by the fact that all patients will have a minimum background therapy of low dose ICS (monotherapy or in combination with LABA, depending on treatment arm).

The potential benefit for the patient includes an improvement in the pulmonary function testing and a potential translation into better asthma control, such as reductions in symptoms and rescue medication use, and improved quality of life. A thorough medical evaluation of the patient's disease and close clinical monitoring for the duration of the study may be considered as additional benefit to the patient.

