• A one-time repeat of percent predicted FEV₁ (pre-bronchodilator FEV₁) is allowed at Visit 101 as well as at Visit 102. Repeat of Visit 101 spirometry should be done in an ad-hoc visit to be scheduled on a date (preferably within 5 days of original Visit 101) that would provide sufficient time to receive confirmation from the spirometry data central reviewer of the validity of the assessment before randomization. Run-in medication should be dispensed only once the repeat spirometry was qualified by spirometry equipment, if all inclusion at Visit 101 are successful in case of necessary repeat of Visit 101.

A one-time re-screen is allowed in case the patients fail to meet the criteria at the repeat, provided the patients return to their previous treatment until re-screened. In this circumstance, patients are not required to go back on prior medication for 1 full month duration as outlined in inclusion criterion 4.

- 8. Patients who demonstrate an increase in FEV₁ of \geq 12% and \geq 200 mL within 15 to 30 minutes after administration of 400 microgram salbutamol / 360 microgram albuterol (or equivalent dose) at Visit 101. Spacers may be used for reversibility testing.
 - All patients must perform a reversibility test at Visit 101.

If reversibility is not demonstrated at Visit 101:

- Reversibility should be first repeated once.
- If the retest does not show reversibility, patients may be permitted to enter the study with documented historical evidence of reversibility that was performed according to American Thoracic Society (ATS) / European Respiratory Society (ERS) guidelines within 2 years prior to Visit 1.
- Alternatively, patients may be permitted to enter the study with a historical positive broncho-provocation test that was performed within 2 years prior to Visit 1.

If reversibility is not demonstrated at Visit 101 (or after repeated assessment at ad-hoc visit) and historical evidence of reversibility / broncho-provocation not available (or not performed according to ATS/ERS guidelines) patients will be noted as screen failure.

Spacer devices are ONLY permitted during reversibility testing. The decision whether or not to use a spacer for the reversibility testing will be taken by the study investigator.

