- 17. History of malignancy of any organ system (other than localized basal cell carcinoma of the skin or *in-situ* cervical cancer), treated or untreated, within the past 5 years, regardless of whether there is evidence of local recurrence or metastases.

- 18. Patients with a history of hypersensitivity or intolerance to any of the study drugs (including excipients) or to similar drugs within the class including untoward reactions to sympathomimetic amines or inhaled medication or any component thereof. This criteria also applies to rescue and Run-in medications.
- 19. Patients with diagnosed rare hereditary problems of galactose intolerance, the Lapp lactase deficiency or glucose-galactose malabsorption or with known intolerance to lactose or milk products.
- 20. Patients who have not achieved acceptable spirometry results at Visit 101 even after a retest, in accordance with American Thoracic Society/European Respiratory Society (ATS/ERS) criteria for acceptability and repeatability, repeat spirometry may be allowed in an ad-hoc visit which should be scheduled as close as possible to the first spirometry attempt (but not on the exact same day) if the spirometry did not qualify due to ATS/ERS criteria at Visit 101 and/or Visit 102. Should the patient fail the repeat assessment, he/she can be rescreened once, provided the patient returns to the prior treatment until re-screened.
- 21. Patients receiving any asthma-related medications in the classes specified in Table 5-1 unless they undergo the required washout period prior to Visit 101 and Visit 201 and follow the adjustment to treatment program.
- 22. Patients receiving any medications in the classes listed in Table 5-2.
- 23. Patients receiving medications in the classes listed in Table 5-3 should be excluded unless the medication has been stabilized for the specified period and the stated conditions have been met.
- 24. Patients with severe narcolepsy and/or insomnia.
- 25. Patients on Maintenance Immunotherapy (desensitization) for allergies for less than 3 months prior to Visit 101 or patients on Maintenance Immunotherapy for more than 3 months prior to Visit 101 but expected to change throughout the course of the study.
- 26. Patients, who are serving a custodial sentence, do not have a fixed residence or who are detained under local mental health legislation/regulations.
- 27. Patients who are directly associated with any members of the study team or their family members.

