5.5.8 Prohibited medication

Prohibited medications, as listed in Table 5-1, must not be taken during the study (unless for the treatment of asthma exacerbations). The specified minimum washout periods prior to Runin (Visit 101) and/or Randomization (Visit 201) are described in Table 5-1. The classes of medication listed in Table 5-2 are not permitted to be taken during the study. The medications in Table 5-3 are only permitted under the circumstances given. Each concomitant drug must be individually assessed against all exclusion criteria and the tables below to see if it is allowed. If in doubt, the investigator should contact the medical monitor before randomizing a patient or allowing a new medication to be started.

If a patient takes systemic corticosteroids within 7 days prior to a study visit, the visit must be rescheduled to allow a washout of 7 days.

Page 38

Table 5-1 **Prohibited Asthma-Related Medications**

lable 5-1 Pronibited Asthma-Relate	ed Medications
Class of medication	Minimum washout period prior to Run-in (V101) 1, 2, 3, 4
Short acting anticholinergics (SAMA)	Must be discontinued 8 hours prior to Visit 101
Fixed combinations of β_2 -agonists and inhaled corticosteroids	Must be discontinued 48 hours prior to Visit 101; Patients should continue with an ICS until Visit 101 when patients will be switched to fluticasone propionate 100 µg b.i.d. (or equivalent dose) for Runin; the last dose of Run-in medication will be taken in the morning of visit 102
Inhaled corticosteroids ¹	All patients must be treated for asthma with fluticasone propionate 100 microgram b.i.d. (or equivalent dose) from Visit 101 to Visit 102 (Figure 3-1); all other ICS must be discontinued at Visit 101
Fixed combinations of short-acting β_2 -agonist and short-acting anticholinergic	Must be discontinued 8 hours prior to Visit 101
Leukotriene Receptor Antagonist (LTRA) and leukotriene synthesis inhibitors	Must be discontinued 7 days prior to Run-in (Visit 101)
Long-acting β ₂ -agonists (LABAs)	LABAs b.i.d. must be discontinued 48 hours prior to Visit 101. LABAs o.d. (i.e., indacaterol) must be discontinued at Visit 1 (14 days prior to Visit 101). All patients will be provided with SABA at Visit 1 for use throughout the study
Salbutamol/albuterol (SABA) provided at Visit 1 and throughout study as required for rescue medication	Must be withheld 6 hours prior to Visit 101 and Randomization (Visit 201) ⁴

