Short acting β_2 -agonists (SABAs) (other than Salbutamol/albuterol provided at Visit 1 for rescue medication)	Must be discontinued at Visit 1 and are not permitted during the study
Parenteral or oral corticosteroids (systemic corticosteroids are permitted for the treatment of asthma exacerbations)	Must be discontinued 4 weeks prior to Run-in (Visit 101)
Intra-muscular depot corticosteroids	Must be discontinued 3 months prior to Run-in (Visit 101)
Monoclonal Antibody: IgE inhibitors and other asthma-related biologics (i.e., omalizumab), IL-5 inhibitors (e.g., mepolizumab)	Must be discontinued 4 months prior to Run-in (Visit 101)
Xanthines	Must be discontinued 7 days prior to Run-in (Visit 101)
Systemic mast cell stabilizers (e.g., cromoglycate, nedocromil, ketotifen)	Must be discontinued 7 days prior to Run-in (Visit 101)

¹ ICS must be discontinued at Visit 101. Treatment for recorded asthma exacerbation as defined in Section 6.4.9 is allowed ONLY until the asthma exacerbation is resolved (minimum wash-out of 7 days is required before scheduling a visit including spirometry assessment).

² This table is not considered all-inclusive. Medications should be assessed for adherence to the indication and other inclusion/exclusion criteria.

Table 5-2 Prohibited Medications

Class of medication	Minimum cessation period prior to Run-in (Visit 101)
Non-potassium sparing diuretics (unless administered as a fixed-dose combination with a potassium conserving drug	7 days
Non-selective systemic β-blocking agents	7 days
Cardiac anti-arrhythmics Class Ia	7 days
Cardiac anti-arrhythmics Class III	7 days, amiodarone 3 months
Other drugs with potential to significantly prolong the QT interval	14 days or 5 half-lives, whichever is longer
Strong inhibitors of cytochrome P4503A (e.g., ketoconazole)	7 days
Tricyclic antidepressants (tetracyclics which are similar in class with regards to drug interaction are also to be excluded)	14 days
Other investigational drugs	30 days or 5 half-lives, whichever is longer
Noradrenaline reuptake inhibitors	7 days
Live attenuated vaccine	30 days

Table 5-3 Medications Allowed Under Certain Conditions

iddic 0-0 Micalcations Anonca on	aci ocitalii ooliaitiolis
Class of medication	Condition
Mucolytic agents not containing bronchodilators	If stabilized for at least 4 weeks prior to Visit 1 and throughout the trial

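### When Visit 101 or Visit 102 spirometry is repeated on a later day, the ICS stop and start rules conflict, and after a Visit 102 repeat entry and baseline values are not tied to one day

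*Protocol*

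**What the plan says.** **Visit 101.** Protocol Table 5-1 (section 5.5.8) states that "all other ICS must be discontinued at Visit 101". Footnote 1 repeats the stop and relaxes it only for treatment of an exacerbation. Inclusion criterion 7 (section 4.1) allows one repeat of percent-predicted FEV1 at each of Visits 101 and 102. The Visit 101 repeat is at a separate ad-hoc visit, for which 5 days is a preference and not a limit. Criterion 7 adds: "Run-in medication should be dispensed only once the repeat spirometry was qualified by spirometry equipment". Going back to previous treatment is mentioned only for patients who fail the repeat and wait to be re-screened.

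**Visit 102.** Section 3.1 ends run-in fluticasone at Visit 102, and the ICS/LABA row of Table 5-1 specifies that "the last dose of Run-in medication will be taken in the morning of visit 102". Exclusion criterion 20 (section 4.2) permits a repeat when spirometry at Visit 101 and/or 102 did not meet ATS/ERS criteria, and wants it "scheduled as close as possible to the first spirometry attempt (but not on the exact same day". Only patients eligible at Visit 102 are randomized, and "Visit 102 (end of Run-in) and Visit 201(Randomization) must take place sequentially on the same day".

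**Text pointing the other way.** Table 5-1 requires fluticasone for all patients between Visits 101 and 102 and describes Visit 101 as a switch from one ICS to the other. Criterion 7 keeps the ICS going in ICS/LABA users while the LABA is withheld. Section 3.6 says: "At no time during the study will any patient be without treatment for asthma".

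**Baselines.** SAP 2.1.1.2 averages diary data over the last 21 run-in days, up to the day before first dose. SAP 2.5.1 takes baseline FEV1 from the two pre-dose readings on Day 1. SAP 2.6.1 takes the Day 1 pre-dose ACQ-7 score and, if it is missing, the last one from Visit 101 or an unscheduled run-in visit.

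**The concern.** A site that follows each rule to the letter stops one ICS before it may start the next, in patients selected for being symptomatic. LABA and leukotriene antagonists are already washed out by then, so rescue SABA is all that is provided for. The text neither sanctions this interval nor prevents it, and sites may resolve it differently.

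There is a smaller measurement problem at Visit 102. The trial asks what a LABA adds in patients inadequately controlled on low-dose ICS. If spirometry is repeated on a later day, the entry ACQ-7 may come from the original day on ICS, and the qualifying and baseline FEV1 from the repeat day off ICS. ACQ-7 is the key secondary endpoint, and its baseline is a model covariate.

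**Working it through.** There is no planned figure to reproduce, so the check sets the rules side by side and counts the days.

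| Step | Visit 101 repeated | Visit 102 repeated (ATS/ERS failure) |
|---|---|---|
| Previous ICS stops | At Visit 101 (Table 5-1, footnote 1) | Morning of Visit 102 (Table 5-1; section 3.1) |
| Repeat takes place | Ad-hoc visit, 5 days preferred (criterion 7); not the same day for an ATS/ERS failure (exclusion 20) | A different day (exclusion 20) |
| Next ICS starts | After the repeat qualifies (criterion 7) | Evening of Visit 201, once eligible (section 3.1) |
| Cover in between | None stated except rescue SABA | None stated except rescue SABA |
| Longest interval | None stated | None stated |

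**Doses.** Fluticasone is twice daily, so a delay of d days is 2 × d doses.
- Visit 101, preferred timing: d = 1 gives 2 × 1 = 2 doses, and d = 5 gives 2 × 5 = 10.
- Visit 102: the normal hand-over is a morning fluticasone dose and an evening dose of study drug. A repeat d days later omits that evening's dose and every dose up to the morning of the repeat day, again 2 × d. The minimum, d = 1, is 2 doses.

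**The conflict within Table 5-1.** The table requires fluticasone from Visit 101 to Visit 102. A site that withholds it until the repeat qualifies, as criterion 7 asks, cannot meet that requirement if the original visit counts as Visit 101.

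**Diary baseline after a Visit 102 repeat.** If run-in is taken to last until the day before first dose, a delay of d days puts d affected days into the 21-day window: the original Visit 102 day, with its evening dose missed, and d − 1 further days. For d = 1 this is 1/21 = 4.8%. For d = 5, borrowing the Visit 101 preference because none is given for Visit 102, it is 5/21 = 23.8%.

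**ACQ-7 baseline after a Visit 102 repeat.** Table 6-1 schedules ACQ-7 at Visits 101 and 102, not at 201. If first dose moves to the repeat day and ACQ-7 is not repeated, there is no Day 1 score. The SAP 2.6.1 fallback does not name Visit 102, so taken literally it can reach back to Visit 101, before the run-in. The general rule in SAP 2.1.1.2 (last value before first dose) would instead pick the original Visit 102 score. The two rules give different covariates.

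**Number of patients.** No repeat rate is given. An assumed 5% to 15% of 750 would be 0.05 × 750 = 37.5 to 0.15 × 750 = 112.5, about 38 to 113. That pools both visits and takes every repeat to be on a later day with ICS stopped. Nothing below rests on it.

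**The case against.** The strongest reply is that the repeat is itself the operative visit. Criterion 7 distinguishes an original Visit 101 from its repeat, section 3.1 admits patients to run-in only once the spirometry criteria are met, and Table 5-1 describes a switch. On that reading the prior ICS runs until the repeat and there is no gap. This is reasonable and probably what was intended, but no passage says it, and the stop rule in footnote 1 has no exception for a repeat.

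For Visit 102, the same-day rule implies that a later randomization makes the repeat day Visit 102, where ACQ-7 is required. ACQ item 7 is scored from FEV1 % predicted and may not be missing (SAP 2.6.1), so unacceptable spirometry may leave no valid score on the original day. Both points have force. They are inferences, though, and they support writing the rule down.

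Four stronger readings are tempting, and the documents do not support them:

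- *Patients enter the trial off ICS after a Visit 101 repeat.* A three-week fluticasone run-in follows, and both FEV1 and ACQ-7 must qualify again at Visit 102.
- *A patient with FEV1 at or above 90% predicted at Visit 102 drifts into range off ICS before a later repeat.* The different-day rule covers only ATS/ERS failures. Criterion 7 gives no timing for a percent-predicted repeat at Visit 102, and no figure supports the drift.
- *Section 3.6 is literally breached.* Its sentence follows one about rescue medication, which every patient has from Visit 1. The conflict is with its intent.
- *Time without LABA is an added harm.* A 48-hour washout plus 5 days gives 2 + 5 = 7 days, but every patient is off LABA throughout run-in by design. Criterion 7 also refers washouts longer than listed to the medical monitor.

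**Conclusion.** The concern stands as a conflict in the text with limited reach. Read literally, a later-day repeat leaves a patient with rescue SABA only: 1 to 5 days after Visit 101 on the preferred timing, and at least 1 day after Visit 102 for an ATS/ERS failure, with no maximum at either. This contradicts the fluticasone requirement in Table 5-1 and the intent of section 3.6 and criterion 7. It assumes that sites treat the original visit as Visit 101 or 102, which the documents neither confirm nor exclude.

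A reader might infer that the treatment comparison is compromised. It is not: any gap comes before randomization, so it does not bias one arm against the other, and baseline FEV1 is a covariate in the primary model. What remains is patient safety and, after a Visit 102 repeat, entry and baseline values that may come from different days and treatment states. The number of patients is unknown, and only those with a repeat on another day are affected. The change is worth making because it is cheap and concerns controller therapy in symptomatic patients.

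**What to change.** 1. Reconcile Protocol sections 3.1, 3.6, 4.1 (criterion 7), 4.2 (exclusion 20) and 5.5.8 (Table 5-1 and footnote 1) so that they give one consistent account of controller treatment between an original Visit 101 or 102 and its repeat. Which clinical rule applies is for the sponsor to decide.
2. State that after a different-day repeat of Visit 102, the repeat day is Visit 102/201.
3. Re-administer ACQ-7 on that day, apply the existing entry criterion of at least 1.5 to that score, and use it as the baseline. Align the fallback in SAP 2.6.1 with this.

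Item 1 is needed as well as item 3. ACQ-7 has a one-week recall, so a repeated questionnaire aligns the day, but the treatment state is settled only when the controller rules are consistent.

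The cost is wording in a few sections, one extra questionnaire for each patient with a later-day Visit 102 repeat, and possibly a few more screen failures.

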4.2 Exclusion criteria

Patients fulfilling any of the following criteria are not eligible for inclusion in this study. No additional exclusions may be applied by the investigator, in order to ensure that the study population will be representative of all eligible patients.

- 1. Patients who have smoked or inhaled tobacco products (including electronic cigarettes) within the 6 month period prior to Visit 1, or who have a smoking history of greater than or equal to 10 pack years (Note: 1 pack is equivalent to 20 cigarettes. 10 pack years = 1 pack /day x 10 years, or ½ pack /day x 20 years.).
- 2. Patients who have had an asthma attack/exacerbation requiring systemic steroids or hospitalization (> 24 hours) or emergency room visit (≤ 24 hours) as follows:
- For adults: within 6 weeks of Visit 1 (Screening). If patients experience an asthma attack/exacerbation requiring systemic corticosteroids or emergency room visit between Visit 1 and Visit 102 they may be re-screened 6 weeks after recovery from the exacerbation.
- For adolescents: Severe asthma attack/exacerbation requiring systemic corticosteroids in the last 6 months, OR hospitalization (> 24 hours) due to severe asthma attack/exacerbation requiring systemic corticosteroids in the last 6 months, OR emergency room visit (≤ 24 hours) due to severe asthma attack/exacerbation requiring systemic corticosteroids within the last 6 months.
- 3. Patients who have ever required intubation for a severe asthma attack/exacerbation.

- 4. Patients who have a clinical condition which is likely to be worsened by ICS administration (e.g., glaucoma, cataract and fragility fractures) who are according to investigator's medical judgment at risk participating in the study).
- 5. Patients who have had a respiratory tract infection or asthma worsening as determined by the investigator within 4 weeks prior to Visit 1 (Screening) or between Visit 1 and Visit 102. Patients may be rescreened 4 weeks after recovery from their respiratory tract infection or asthma worsening.
- 6. Patients with evidence upon visual inspection (laboratory culture is not required) of clinically significant (in the opinion of investigator) or opharyngeal candidiasis at Visit 102 or earlier, with or without treatment. Patients may be rescreened once their candidiasis has been treated and has resolved.
- 7. Patients with any chronic conditions affecting the upper respiratory tract (e.g., chronic sinusitis) which in the opinion of the investigator may interfere with the study evaluation or optimal participation in the study.
- 8. Patients with a history of chronic lung diseases other than asthma, including (but not limited to) COPD, sarcoidosis, interstitial lung disease, cystic fibrosis, clinically significant bronchiectasis and active tuberculosis.
- 9. Patients with Type I diabetes or uncontrolled Type II diabetes.
- 10. Patients who have a clinically significant laboratory abnormality at Visit 101.
- 11. Use of other investigational drugs within 30 days of Visit 101 or 5 half-lives whichever is longer or until the expected pharmacodynamics effect has returned to baseline.
- 12. Patients who, either in the judgment of the investigator or the responsible Novartis personnel, have a clinically significant condition such as (but not limited to) unstable ischemic heart disease, New York Heart Association (NYHA), Class III/IV left ventricular failure arrhythmia, uncontrolled hypertension, cerebrovascular disease, psychiatric disease, neurodegenerative diseases, or other neurological disease, uncontrolled hypo- and hyperthyroidism and other autoimmune diseases, hypokalemia, hyperadrenergic state, or ophthalmologic disorder or patients with a medical condition that might compromise patient safety or compliance, interfere with evaluation, or preclude completion of the study.
- 13. Patients with a history of myocardial infarction (clinical confirmation by the study investigator required) within the previous 12 months.
- 14. Concomitant use of agents known to prolong the corrected QT (QTc) interval unless it can be permanently discontinued for the duration of study.
- 15. Patients with a history of long QT syndrome or whose QTc measured at Visit 101 (Fridericia method) is prolonged (> 450 msec for males and > 460 msec for females) and confirmed by a central assessor or inability to determine the QTcF interval (these patients should not be re-screened).
- 16. Patients who have a clinically significant ECG abnormality at Visit 101 (Start of Run-in/Baseline epoch) and/or any time prior to randomization (Visit 102), including unscheduled ECG. ECG evidence of myocardial infarction at Visit 101 (via central reader) should be clinically assessed by the study investigator with supportive documentation.
- 17. History of malignancy of any organ system (other than localized basal cell carcinoma of the skin or *in-situ* cervical cancer), treated or untreated, within the past 5 years, regardless of whether there is evidence of local recurrence or metastases.

- 18. Patients with a history of hypersensitivity or intolerance to any of the study drugs (including excipients) or to similar drugs within the class including untoward reactions to sympathomimetic amines or inhaled medication or any component thereof. This criteria also applies to rescue and Run-in medications.
- 19. Patients with diagnosed rare hereditary problems of galactose intolerance, the Lapp lactase deficiency or glucose-galactose malabsorption or with known intolerance to lactose or milk products.
- 20. Patients who have not achieved acceptable spirometry results at Visit 101 even after a retest, in accordance with American Thoracic Society/European Respiratory Society (ATS/ERS) criteria for acceptability and repeatability, repeat spirometry may be allowed in an ad-hoc visit which should be scheduled as close as possible to the first spirometry attempt (but not on the exact same day) if the spirometry did not qualify due to ATS/ERS criteria at Visit 101 and/or Visit 102. Should the patient fail the repeat assessment, he/she can be rescreened once, provided the patient returns to the prior treatment until re-screened.
- 21. Patients receiving any asthma-related medications in the classes specified in Table 5-1 unless they undergo the required washout period prior to Visit 101 and Visit 201 and follow the adjustment to treatment program.
- 22. Patients receiving any medications in the classes listed in Table 5-2.
- 23. Patients receiving medications in the classes listed in Table 5-3 should be excluded unless the medication has been stabilized for the specified period and the stated conditions have been met.
- 24. Patients with severe narcolepsy and/or insomnia.
- 25. Patients on Maintenance Immunotherapy (desensitization) for allergies for less than 3 months prior to Visit 101 or patients on Maintenance Immunotherapy for more than 3 months prior to Visit 101 but expected to change throughout the course of the study.
- 26. Patients, who are serving a custodial sentence, do not have a fixed residence or who are detained under local mental health legislation/regulations.
- 27. Patients who are directly associated with any members of the study team or their family members.
- 28. Patients unable to use the Concept1 dry powder inhaler, Twisthaler[®], Accuhaler[®] or MDI. Spacer devices are not permitted for rescue medication.
- 29. History of alcohol or other substance abuse in the last 10 years.
- 30. Patients with a known history of non-compliance to medication or who were unable or unwilling to complete a patient diary or who are unable or unwilling to use Electronic Peak Flow with eDiary device.
- 31. Patients who do not maintain regular day/night, waking/sleeping cycles (e.g., night shift workers).
- 32. Pregnant or nursing (lactating) women, where pregnancy is defined as the state of a female after conception and until the termination of gestation, confirmed by a positive human Chorionic Gonadotropin (hCG) laboratory test.
- 33. Women of child-bearing potential, defined as all women physiologically capable of becoming pregnant, **unless** they are using highly effective methods of contraception while taking study treatment and for 30 days after stopping medication.

Highly effective contraception methods include:

- Total abstinence (when this is in line with the preferred and usual lifestyle of the subject. Periodic abstinence (e.g., calendar, ovulation, symptothermal, post-ovulation methods) and withdrawal are not acceptable methods of contraception
- Female sterilization (have had surgical bilateral oophorectomy with or without hysterectomy), total hysterectomy, or tubal ligation at least six weeks before taking study treatment. In case of oophorectomy alone, only when the reproductive status of the woman has been confirmed by follow up hormone level assessment
- Male sterilization (at least 6 months prior to screening). For female patients on the study, the vasectomized male partner should be the sole partner for that patients
- Use of oral, (estrogen and progesterone), injected or implanted hormonal methods of contraception or placement of an intrauterine device (IUD) or intrauterine system (IUS), or other forms of hormonal contraception that have comparable efficacy (failure rate <1%), for example hormone vaginal ring or transdermal hormone contraception.

In case of use of oral contraception women should have been stable on the same pill for a minimum of 3 months before Visit 201 (Randomization/Start of treatment epoch).

Women are considered post-menopausal and not of child-bearing potential if they have had 12 months of natural (spontaneous) amenorrhea with an appropriate clinical profile (e.g., age appropriate, history of vasomotor symptoms) or have had surgical bilateral oophorectomy (with or without hysterectomy), total hysterectomy, or tubal ligation at least six weeks ago. In the case of oophorectomy alone, only when the reproductive status of the woman has been confirmed by follow-up hormone level assessment is she considered not of child-bearing potential.

If requested by local authorities/ethics committees, additional and more frequent pregnancy testing might be performed.

34. Use of Long Acting Muscarinic Antagonist (LAMA) within 3 months prior to Visit 1.

5 Treatment

